1.2 Study Objectives

Objectives	Endpoints
Primary Objective	Primary Endpoint

To investigate the efficacy of an experimental dentifrice containing 1150 ppm fluoride and 5% KNO₃ to enhance remineralization of enamel compared to a placebo dentifrice (0ppm fluoride) after 4 hours of intra-oral exposure.	
%SMHR at 4 hrs.
Secondary Objectives	Secondary Endpoints
Efficacy	

To investigate the efficacy of an experimental dentifrice containing 1150 ppm fluoride and 5% KNO₃ to inhibit demineralization of enamel compared to a placebo dentifrice (0ppm fluoride) after 4 hours of intra-oral exposure.To investigate the efficacy of an experimental dentifrice containing 1150 ppm fluoride and 5% KNO₃ to enhance remineralization of enamel compared to a marketed, reference dentifrice containing 1100ppm fluoride after 4 hours of intra-oral exposure.To investigate the efficacy of an experimental dentifrice containing 1150 ppm fluoride and 5% KNO₃ to enhance remineralization of enamel compared to a placebo dentifrice (0ppm fluoride) and a marketed, reference dentifrice containing 1100ppm fluoride after 12 hours of intra-oral exposure.To investigate the efficacy of an experimental dentifrice containing 1150 ppm fluoride and 5% KNO₃ to inhibit demineralization of enamel compared to a reference dentifrice containing 1100ppm fluoride after 4 hours of intra-oral exposure.To investigate the efficacy of an experimental dentifrice containing 1150 ppm fluoride and 5% KNO₃ to inhibit demineralization of enamel compared to a placebo dentifrice (0ppm fluoride) and a marketed, reference dentifrice containing 1100ppm fluoride after 12 hours of intra-oral exposure.To investigate the efficacy of an experimental dentifrice containing 1150 ppm fluoride and 5% KNO₃ to promote fluoride uptake in enamel compared to a placebo dentifrice (0ppm fluoride) and a marketed, reference dentifrice containing 1100ppm fluoride after 4 and 12 hours of intra-oral exposure.To investigate the efficacy of an experimental dentifrice containing 1150 ppm fluoride and 5% KNO₃ to reduce future acid-induced demineralization in enamel compared to a placebo dentifrice (0ppm fluoride) and a marketed,	
%RER at 4 hrs.%SMHR at 4 hrs.%SMHR at 12 hrs.%RER at 4 hrs.%RER 12 hrs.EFU at 4 and 12 hrs.ARR at 4 and 12 hrs.

Property of Haleon
Confidential

May not be used, divulged, published, or otherwise disclosed
without the consent of Haleon

CCI

Statistical Analysis Plan Template v7.0

Page 9 of 43

Objectives	Endpoints
reference dentifrice containing 1100ppm fluoride after 4 and 12 hours of intra-oral exposure.	

 To investigate the efficacy of a marketed, reference dentifrice containing 1100ppm fluoride, to enhance remineralization, inhibit demineralization, to reduce future acid-induced demineralization and to promote fluoride uptake in enamel compared to a placebo dentifrice (0ppm fluoride) after 4 and 12 hours of intra-oral exposure. 	
 %SMHR, %RER, EFU, ARR at 4 and 12 hrs.
Safety	

 To assess the oral tolerability of an experimental dentifrice containing 1150ppm fluoride and 5% KNO₃. 	
 Treatment emergent adverse events
Exploratory Objectives	Exploratory Endpoints

 To calculate the proportion of subjects who evidence a RER ratio (%RER 0ppm fluoride placebo and 5% KNO₃ : %RER experimental dentifrice containing 1150 ppm fluoride) ≥ 3 and ≥ 2.5 	
 %RER at 4 and 12 hrs.

1.3 Treatments

Test Dentifrice	Placebo Control	Reference Dentifrice
Experimental Dentifrice containing 1150ppm fluoride and 5% KNO ₃ *	0ppm fluoride dentifrice containing 5% KNO ₃	Crest Pro-Health Densify Daily Protection

* KNO₃ is commonly used in other marketed anti sensitive toothpaste.

All dentifrices will be applied in the same manner by brushing 1.5±0.1g of dentifrice on to the buccal surfaces of their natural teeth for 25 timed seconds and then swishing the resulting dentifrice slurry around the mouth, without further brushing, for a timed period of 95 seconds.

Subjects will use a 0ppm fluoride washout dentifrice twice daily for 2 days prior to each treatment visit in place of their usual oral hygiene practice.

All subjects will be centrally randomized to 1 of 6 sequences using an Interactive Response Technology (IRT) based on a schedule consisting of randomized blocks of 6-sequences from a 3-treatment Williams Square design.

All study site staff will be blinded except for those staff members directly dealing with dispensing study products. Site staff, study statistician(s), data management staff and other employees of the sponsor and vendors acting on behalf of the sponsor, who may influence study outcomes will be blinded to the product allocation.

1.4 Sample Size Calculation

A sufficient number of healthy subjects will be screened to ensure that up to 33 subjects will be randomized to participate in the study to ensure at least 30 evaluable subjects complete the study. With a sample size of 30 subjects completing the study, there will be 97% power to detect

a difference in means of 7.5% in %SMHR at 12 hours, assuming a standard deviation (SD) of differences of 9.94% using a paired t-test with a 0.05 two-sided significance level.

These differences and variability were observed when comparing a similar test product to a similar Placebo Control and Reference Dentifrice at 4 hours in GSKCH study 208166. In the absence of any historical studies with results at 12 hours, the result at 12 hours will be assumed to be similar to 4 hours for the purpose of sample size calculation.

A recent network meta-analysis (Haleon study 300033) across 14 studies using the same design involving 22 different grouped type of study products suggests a SD of differences as high as 12.16% at 4 hours. Even with such a higher SD, there would still be 90% (80%) power to detect a difference in means of 7.5% (6.5%) in %SMHR at 12 hours.

Previous Haleon study 208166 and network meta-analysis 300033 suggest respective SD of differences for %RER between 17.5% and 20.3%. Such estimates of variability would give 90% (80%) power to detect respective difference in means of 10.7% and 12.4% (9.3% and 10.7%).

2 Planned Analyses

2.1 Interim Analysis

No interim analysis is planned.

2.2 Final Analyses

The final planned primary analyses will be performed after the completion of the following sequential steps:

1. All subjects have completed the study as defined in the protocol.
2. All required database cleaning activities including any external data reconciliation and a Blind Data Review (BDR) Meeting have been completed.
3. Database has been locked.
4. All criteria for unblinding the randomization codes have been met and the randomization codes have been distributed.

3 Considerations for data analyses and Data Handling Conventions

3.1 Baseline Definition

Other than the Baseline indentation lengths (see section 4.4) there will be no definition of Baseline used in this study.

3.2 Timepoints and Visit Windows

Visits and assessments will be conducted in line with the Schedule of Activities (section 1.1) and any which are out-of-window will be recorded as protocol deviations and assessed for exclusion from the Per-Protocol (PP) Population (section 4.1.2). Otherwise, the results from each scheduled visit and assessment will directly represent the result at the respective time-point in all analyses.

4 Data Analysis

Data analysis will be performed by the **CCI** **CCI**. The statistical analysis software used will be SAS version 9.4 in Windows environment.

Prior to database closure a Blind Data Review Meeting (BDRM) will be conducted in which various aspects of the trial will be discussed and agreed.

Except as described below, all listings will be produced for all randomized subjects.

4.1 Populations for Analysis

Tables described in this section will be produced for all randomized subjects.

4.1.1 Subject Disposition

Subject disposition will be summarized as the number and percentage of subjects who complete the study, with the number who discontinue broken down by reason for discontinuation, by treatment group across study treatment periods (Table 14.1.1) and by sequence group and period (Table 14.1.2). Subject disposition including the subject status (completer, Yes/No), critical demographic data (age, sex, race), the timing of the discontinuation, treatment sequence group, and the specific reason for discontinuation will be listed for all subjects in the Screened population in Listing 16.2.1.1.

4.1.2 Protocol Deviations

Protocol deviations will be tracked by the study team throughout the conduct of the study. Data will be reviewed prior to unblinding and closure of the database to ensure all important deviations are captured and categorised.

Each PD will be assessed as part of the BDR, but possible PDs (list not exhaustive) which may impact the reliability of erosion parameters are non-compliance with the use of study product at the visit, lifestyle considerations or instructions for removal and return of palatal appliance, and therefore will be excluded from the per-protocol population (See Section 4.1.3).

The number and percentage of subjects with any important protocol deviations and with each type of important protocol deviations will be presented by treatment (Table 14.1.3) and listed in Listing 16.2.2.2.

4.1.3 Analysis Populations

The following analysis populations will be defined:

- The Screened population will include all subjects who are screened.
- The Intent-to-Treat (ITT) population will include all subjects who are randomized. Study product group will be assigned to each visit for analyses based on the study product sequence the subject was randomized to.
- The Safety population will include all randomized subjects who receive at least 1 dose of study product. Study product group will be assigned for analyses based on the last known study product the subject actually received prior to the safety event.
- The Per-Protocol (PP) population will include all subjects from the ITT population who have at least one visit with non-missing erosion parameters unaffected by protocol deviations. Study product group will be assigned to each visit for analyses based on the study product the subject received.

Subjects excluded from any of the ITT, Safety and PP analysis populations will be listed for all subjects in the Screened population in Listing 16.2.3, with the reason for exclusion.

4.2 Subject Demographics and Other Baseline Characteristics

4.2.1 Demographic Characteristics

Demographic data (age, sex, race, ethnicity) will be summarized descriptively.

4.2.2 General Medical History

Medical history will be collected in the CRF.

4.3 Treatments (Study Product, Rescue Medication, other Concomitant Therapies, Compliance)

4.3.1 Study Product Compliance and Exposure

Non-compliance with study product will be captured as a PD and summarized.

4.3.2 Prior and Concomitant Medication

All prior and concomitant medications will be collected in the CRF.

4.3.3 Medical Device Incidents and Malfunctions

The toothbrushes to be used in this study are medical devices.

All device deficiencies, (including malfunction, use error and inadequate labelling) shall be documented, and reported by the investigator throughout the clinical investigation and appropriately managed by the sponsor.

4.4 Analysis of Efficacy

Statistical testing of all endpoints in this study will be conducted at a two-sided significance level of 0.05. A sequential testing strategy will be applied to preserve the overall type-1 error control for the respective sequential comparisons between the Experimental dentifrice and Placebo Control at 4 hours for the %SMHR (primary endpoint) and %RER (secondary endpoint). There will be no further adjustments for multiplicity.

All analyses of erosion parameters will be primarily based on the ITT population. If there are more than a 10% of ITT population subjects with at least 1 visit with non-missing erosion parameters deemed to be affected by a protocol deviation, the PP analyses will also be performed as supportive analyses.

Summary statistics including the counts (missing and non-missing), mean, SD, standard error (SE), median, minimum, and maximum will be presented by study product for each parameter for each time-point (4 and 12 hours).

4.4.1 Primary Efficacy Endpoint - %SMHR at 4 hours (Test v Placebo)

4.4.1.1 Primary Efficacy Endpoint Definition

The primary endpoint will be the %SMHR at 4 hours and the comparison between the Experimental dentifrice and Placebo Control.

For each replicate within each specimen (collected after 4 hours *in situ* remineralization) within a particular study visit, the %SMHR (at the replicate level) will be derived as

$$[(E1-R)/(E1-B)] * 100$$

where:

B = indentation length (μm) of sound enamel at baseline

E1 = indentation length (μm) after first erosive challenge

R = indentation length (μm) after 4 hours *in situ* remineralization

The %SMHR at the subject visit level (to be used in the analysis) will be derived as the mean of the specimen means (across evaluable replicate %SMHR within a specimen) within that visit. Missing data or data deemed as non-evaluable by the laboratory will not be used in these derivations.

4.4.1.2 Statistical Hypothesis, Model, and Method of Analysis

The null and alternative hypotheses are:

- H0: there is no difference between the products.
- H1: there is a difference between the products.

A mixed model (including results across all 3 study products) will be used to analyze the %SMHR at 4 hours with fixed effects for treatment and study visit, as well as random effect for subject. Kenward Rogers degrees of freedom approach will be applied. The least square means for each study product will be presented along with the differences between least square means (Experimental dentifrice - Placebo Control; including two-sided p-value and 95% confidence interval) to test for a difference between products.

The assumption of residual normality and variance homogeneity will be investigated from the mixed model through residual plots. If violated, a non-parametric method (Wilcoxon Signed Rank Test) will be performed for each pairwise comparison of interest as supportive analyses.

4.4.2 Secondary Efficacy Variables

4.4.2.1 %SMHR at 4 hours (Test v Reference and Reference v Placebo)

The results from the mixed model applied from the primary analysis for %SMHR at 4 hours will also be used to test and present the pairwise differences in %SMHR at 4 hours between the Experimental dentifrice versus the Reference dentifrice and the Reference dentifrice versus the Placebo Control.

4.4.2.2 %SMHR at 12 hours

4.4.2.2.1 Secondary Efficacy Endpoint Definition

%SMHR at 12 hours: %SMHR at the subject visit level (to be used in the analysis) will be derived from within specimen replicate results in similar fashion to the %SMHR at 4 hours.

For each replicate within each specimen (collected after 12 hours *in situ* remineralization) within a particular study visit, the %SMHR (at the replicate level) will be derived as

$$[(E1-R)/(E1-B)] * 100$$

where:

B = indentation length (μm) of sound enamel at baseline

E1 = indentation length (μm) after first erosive challenge

R = indentation length (μm) after 12 hours *in situ* remineralization

The %SMHR at the subject visit level (to be used in the analysis) will be derived as the mean of the specimen means (across evaluable replicate %SMHR within a specimen) within that visit. Missing data or data deemed as non-evaluable by the laboratory will not be used in these derivations.

4.4.2.2.2 Statistical Hypothesis, Model, and Method of Analysis

The null and alternative hypotheses are:

- H0: there is no difference between the products.
- H1: there is a difference between the products.

The same mixed model as applied for the primary analysis for %SMHR at 4 hours will be applied for the %SMHR at 12 hours. The same 3 pairwise comparisons of interest will be presented.

4.4.2.3 %RER at 4 and 12 hours

4.4.2.3.1 Secondary Efficacy Endpoint Definition

%RER at 4 hours and at 12 hours: The R in the derivation of each secondary endpoint represents the indentation length (μm) after the 4 or 12 hours *in situ* remineralization as appropriate.

The %RER at the subject visit level (to be used in the analysis) will be derived from within specimen replicate results in similar fashion to the %SMHR. The %RER (at the replicate level) will be derived as

$$[(E1-E2)/(E1-B)] * 100$$

where:

B = indentation length (μm) of sound enamel at baseline

E1 = indentation length (μm) after first erosive challenge

E2 = Indentation length (μm) after second erosive challenge.

The %RER at the subject visit level (to be used in the analysis) will be derived as the mean of the specimen means (across evaluable replicate %RER within a specimen) within that visit. Missing data or data deemed as non-evaluable by the laboratory will not be used in these derivations.

4.4.2.3.2 Statistical Hypothesis, Model, and Method of Analysis

The null and alternative hypotheses are:

- H0: there is no difference between the products.
- H1: there is a difference between the products.

The same mixed model as applied for the primary analysis for %SMHR at 4 hours will be applied for %RER at 4 and 12 hours. The same 3 pairwise comparisons of interest will be presented. The residuals from each model will be examined and similar to the primary analysis, supporting non-parametric results be presented if required.

4.4.2.3.3 Exploratory Analysis

The proportion of subjects who evidence a RER ratio (Placebo Control : Experimental dentifrice) ≥ 3 and ≥ 2.5 will be presented along with asymptotic 95% confidence intervals for both 4 and 12 hour time points. Assignments will be made in certain scenarios of RER values at the time point as follows:

- Experimental dentifrice RER ≥ 0 and Placebo Control < 0 = Subject evidenced RER ratio
- Placebo Control ≥ 0 = Subject did not evidence RER ratio

4.4.2.4 % ARR at 4 and 12 Hours

4.4.2.4.1 Secondary Efficacy Endpoint Definition

ARR at 4 hours and at 12 hours: The R in the derivation of each secondary endpoint represents the indentation length (μm) after the 4 or 12 hours *in situ* remineralization as appropriate. The ARR at the subject visit level (to be used in the analysis) will be derived from within specimen replicate results in similar fashion to the %SMHR. The ARR will be derived as

$$1 - [(E2 - R)/(E1 - B)].$$

where:

B = indentation length (μm) of sound enamel at baseline

R = indentation length (μm) after 4 hours or 12 hours *in situ* remineralization

E1 = indentation length (μm) after first erosive challenge

E2 = Indentation length (μm) after second erosive challenge.

The ARR at the subject visit level (to be used in the analysis) will be derived as the mean of the specimen means (across evaluable replicate ARR within a specimen) within that visit. Missing data or data deemed as non-evaluable by the laboratory will not be used in these derivations.

4.4.2.4.2 Statistical Hypothesis, Model, and Method of Analysis

The null and alternative hypotheses are:

- H0: there is no difference between the products.
- H1: there is a difference between the products.

The same mixed model as applied for the primary analysis for %SMHR at 4 hours will be applied for the ARR at 4 and 12 hours. The same 3 pairwise comparisons of interest will be presented. The residuals from each model will be examined and similar to the primary analysis, supporting non-parametric results be presented if required.

4.4.2.5 EFU at 4 and 12 Hours

4.4.2.5.1 Secondary Efficacy Endpoint Definition

EFU at 4 hours and at 12 hours: The EFU result will be received from the laboratory per specimen, pooled across multiple microdrill enamel biopsies within each specimen. The mean across specimens relating to a specific timepoint (4 or 12 hours) will be derived. The natural log of this mean will be used to represent the subject visit level EFU at the timepoint to be used in the analysis.

Missing data or data deemed as non-evaluable by the laboratory will not be used in these derivations.

4.4.2.5.2 Statistical Hypothesis, Model, and Method of Analysis

The null and alternative hypotheses are:

- H0: there is no difference between the products.
- H1: there is a difference between the products.

The same mixed model as applied for the primary analysis for %SMHR at 4 hours will be applied for the EFU at 4 and 12 hours. The same 3 pairwise comparisons of interest will be presented. The residuals from each model will be examined and similar to the primary analysis, supporting non-parametric results be presented if required. The back-transformed values will be presented to represent the least square geometric means and geometric mean ratio (and 95% CIs).

4.4.3 Handling of Missing Values/Censoring/Discontinuations

Exclusions of any data from the analyses will be determined during a Blinded Data Review (BDR) meeting prior to database lock and unblinding.

If it is not possible to derive the erosion parameter at the visit level due to missing data from specimens not collected and/or data deemed to be non-evaluable by the laboratory, the data will be treated as missing in the Intent-To-Treat (ITT) analyses.

4.5 Analysis of Safety

AEs will be regarded as treatment emergent if they occur on or after the date of first use of study product in the study. In this crossover trial, events will be assigned to the study product being received at the onset of the event. Treatment-emergent adverse events (TEAEs) with an onset date/time between visits will be assigned to the study product received in the previous period. TEAEs with an onset after last use of any study product will be assigned to the last study product used.

The number of distinct events and the number and percentage of subjects having at least one event will be presented by study product and overall for the following:

- AEs (overall only)
- SAEs (overall only)
- TEAEs
- Serious TEAEs
- Oral TEAEs
- Product Related TEAEs
- Device related AEs
- Device Incidents

All AEs and device incidents will be listed providing all relevant details collected in the CRF.

5 Changes to the Protocol Defined Statistical Analysis Plan

There were no changes or deviations to the originally planned statistical analysis specified in the protocol/protocol amendment (Dated: DD/MMM/YYYY).

<Compound/Product>

<Protocol Number>

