1.2 Schedule of Activities

The schedule of activities table provides an overview of the subject visits and study procedures.

The investigator may schedule visits (unplanned visits) in addition to those listed on the schedule of activities, to conduct evaluations or assessments required to protect the well-being of the subject.

Procedure/Assessment	Screening	Study Period 1		Study Period 2		Study Period 3	
	Visit 1	Visit 2 (Treatment)	Visit 3 (V2+1day)	Visit 4 (Treatment)	Visit 5 (V4+1day)	Visit 6 (Treatment)	Visit 7 (V6+1day)
Informed consent	X						
Demographics	X						
Medical history	X						
Current/prior/concomitant medication review	X	X	X	X	X	X	X
OST Examination ¹	X	X	X	X	X	X	X
OHT Examination	X						X
Assessment of stimulated and unstimulated saliva flow rate ²	X						
Review of inclusion/exclusion criteria	X						
Try-in of palatal appliance	X						
Subject eligibility	X						
Dispense wash-out products and diary	X						
Diary review		X	X	X	X	X	X
Subject continuance		X	X	X	X	X	X
Randomization to treatment sequence		X					
Place palatal appliance fitted with enamel specimens into subject's mouth ³		X		X		X	
Supervised toothbrushing		X		X		X	
Intra oral phase 4 hours ^{3,4}		X		X		X	

Property of Haleon- Confidential

May not be used, divulged, published or otherwise disclosed without the consent of Haleon

Procedure/Assessment	Screening		Study Period 1		Study Period 2		Study Period 3	
	Visit 1		Visit 2 (Treatment)	Visit 3 (V2+1day)	Visit 4 (Treatment)	Visit 5 (V4+1day)	Visit 6 (Treatment)	Visit 7 (V6+1day)
Intra oral phase 12 hours ^{3,5}			X		X		X	
Adverse events review ⁶	X		X	X	X	X	X	X
Medical device incidents review ¹			X	X	X	X	X	X
Return wash-out products							X	
Return palatal appliance				X		X		X
Study conclusion								X

Abbreviations: OST: Oral Soft Tissue, OHT: Oral Hard Tissue.

Footnotes:

1. At Visits 2, 4 & 6 OST examination will be performed prior to insertion of the appliance and at Visits 3, 5 & 7 when the subject returns their palatal appliance.
2. Re-evaluation of saliva flow may be required within the study should the subject begin a treatment of medications likely to induce xerostomia.
3. Laboratory analysis of enamel specimens performed prior to placing and after removing the specimens from the palatal appliance as described in the separate laboratory procedures document.

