6.7 Compliance

Study products will be administered under the supervision of investigator site personnel. The date and time of each dose/application/administration will be recorded in the source documents or directly in the CRF.

A diary will be supplied to promote compliance and to capture details of use of the washout dentifrice during the 2 days prior to treatment visits. Subjects may also record additional information such as AEs or medications used. Any additional details relevant to efficacy or safety should be reviewed by the investigator (or suitably qualified designee) with the subjects and transcribed to the CRF as appropriate.

The number of any missed or additional applications of the washout dentifrice will be captured as protocol deviations and transcribed from the diary into the CRF. Subjects will be re-instructed in the correct usage requirements and diary completion as needed.

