8.2 Study Period

There will be an interval of at least 3 days between study periods (i.e., administration of subsequent doses of investigational product will not occur until at least 3 days after the previous dose of investigational product). Prior to each treatment visit (Visits 2, 4 & 6), there will be a washout period of a minimum of 3 days. During this period subjects will use their own dentifrice and toothbrush for at least one day, and a 0ppm fluoride washout dentifrice and study toothbrush (provided) for two days immediately prior to the treatment visit (including in the morning of the scheduled visit).

All procedures will be conducted by the Investigator, or suitably qualified designee. To facilitate subject flow, clinical and instrumental assessments may be recorded on a paper source document and later transcribed into the CRF.

8.2.1 Visit 2/Study Period 1

Subjects will undergo, in the following order (wherever possible) and the findings recorded in the CRF.

1. Changes in concomitant medication or non-drug treatments/procedures will be documented.
2. Spontaneous reporting of adverse events and those elicited by asking subjects to respond to a non-leading question such as “How do you feel?” will be assessed and any AEs recorded in the CRF.
3. Subject undergoes an OST examination.
4. Review of subject diary to assess for compliance.
5. Subject continuance assessed.
6. Subjects randomized to treatment periods.
7. Subject has appliance containing enamel blocks fitted.
8. Subject undergoes supervised product application.

Property of Haleon- Confidential

May not be used, divulged, published or otherwise disclosed without the consent of Haleon

9. 4 hours after dentifrice application subject has 4 enamel blocks removed and a 30 ± 10 minute lunch period will be given where the subject does not wear the palatal appliance. After the 30 minute lunch period, subject will brush their teeth and rinse their mouth with water and replace their appliance.
10. AEs and incidents recorded.
11. Subject is allowed to leave site after the 4.5 hour time point. Subject will receive oral and written instructions for dinner (at 8.5 hour time point to 9 hour ± 10 mins time point) and will then brush their teeth and rinse their mouth with water prior to refitting their appliance and instructions/diary for the end of the treatment day (13 hour).

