9.3.1 Oral Soft Tissue (OST) Examination

This procedure will be conducted by a qualified, experienced clinical examiner. The OST examination will be accomplished by direct observation and palpation with retraction aids, as appropriate. The examination will cover the oral labial mucosa (including lips), buccal mucosa, mucogingival folds, gingival mucosa, hard palate, soft palate, tonsillar area, pharyngeal area, tongue, sublingual area, submandibular area and salivary glands. Abnormal findings from the examination will be recorded in the CRF, with details of any abnormalities. The results of the OST examination performed at screening will be used to determine subject eligibility. Any new OST abnormality or worsening of a pre-existing condition observed by the clinical examiner or reported by the subject after the screening examination will be recorded as an AE.

Where possible, this procedure should be conducted by a single clinical examiner.

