12.3.4 Safety Analyses

AEs will be regarded as treatment emergent if they occur on or after the first use of study product in the study. In this crossover trial, events will be assigned to the study product being received at the onset of the event. Treatment-emergent adverse events (TEAEs) with an onset date/time between visits will be assigned to the study product received in the previous period. TEAEs with an onset after last use of any study product will be assigned to the last study product used.

The number of distinct events and the number and percentage of subjects having at least one event will be presented by study product and overall for the following:

- AEs (overall only)
- SAEs (overall only)
- TEAEs
- Serious TEAEs
- Oral TEAEs
- Product Related TEAEs
- Device related AEs
- Device Incidents

All AEs and device incidents will be listed providing all relevant details collected in the CRF.

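### SAP 4.5 starts treatment emergence at the calendar date of first use, not at first use as in the protocol, so an adverse event with onset dated Visit 2 but before brushing becomes treatment emergent, and the change is not declared

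*SAP*

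**What the plan says.** The two documents define a treatment-emergent AE (TEAE) differently.

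- Protocol 12.3.4: "AEs will be regarded as treatment emergent if they occur on or after the first use of study product in the study".
- SAP 4.5: AEs are "regarded as treatment emergent if they occur on or after the date of first use of study product".
- SAP Section 5: "There were no changes or deviations to the originally planned statistical analysis specified in the protocol/protocol amendment".

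The rest of the paragraph on treatment emergence and product assignment is the same in both documents.

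The Visit 2 procedures in Protocol 8.2.1, to be followed in order wherever possible, put AE questioning at step 2, then "Subject undergoes an OST examination" at step 3, randomization at step 6, and "Subject undergoes supervised product application" at step 8. Footnote 1 to the schedule of activities, repeated in the SAP, fixes the timing of the soft tissue (OST) examination: "At Visits 2, 4 & 6 OST examination will be performed prior to insertion of the appliance". Protocol 9.3.1 provides that any new or worsened soft tissue finding "observed by the clinical examiner or reported by the subject after the screening examination will be recorded as an AE". Protocol 10.3 collects AEs from consent.

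**The concern.** A rule based on the calendar date usually differs from one based on first use only by chance. Here the plan schedules AE detection for every subject on the date of first use, before first use. Subjects also brush with the washout paste that morning. An AE that begins then is not treatment emergent under the protocol, and the assigned product cannot have caused it. Under the SAP it is treatment emergent.

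The only safety objective is the oral tolerability of the experimental dentifrice, and its endpoint is treatment-emergent AEs. Table 14.3.1 reports TEAEs and oral TEAEs by product, so the definition decides what enters those rows. SAP Section 5 gives a reader of the study report no notice that the definition moved.

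**Working it through.** No figure in the plan is in dispute. The check sets the two rules side by side and then sizes the difference.

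**Step 1: which events change status.** Take an AE in a subject who first brushes at Visit 2.

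| Recorded onset | Protocol 12.3.4 | SAP 4.5 |
|---|---|---|
| Before the Visit 2 date | Not a TEAE | Not a TEAE |
| Visit 2 date, before brushing | Not a TEAE | TEAE |
| Visit 2 date, after brushing | TEAE | TEAE |
| Later date | TEAE | TEAE |

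Only the second row differs. Both rules turn on when the event occurs, not on when it is found.

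**Step 2: which product such an event is given.** SAP 4.5 assigns events to the product being received at onset. Handled by date, that is the product used on the Visit 2 date. Handled by clock time, no product has been received. The Safety population rule in SAP 4.1.3, the last product actually received before the event, then returns none. The event would be a TEAE with no product column in Table 14.3.1. The SAP does not say which reading applies.

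**Step 3: weight of one event.** Up to 33 subjects are randomized, so each product has at most 33 users. One reclassified subject moves a product's percentage by 1/33 = 3.0 points, or more if fewer subjects receive that product.

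**Step 4: spread over products.** SAP 1.3 allocates in blocks of the 6 Williams sequences, and each product comes first in 2 of the 6. With 33 subjects, about 33/3 = 11 start on each product.

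**Step 5: illustration under assumed rates.** The documents give no rate for AEs with onset on the Visit 2 date before brushing. Let q be the assumed proportion of subjects with one, and read assignment by date.

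- Expected extra subjects overall = 33q.
- Expected extra per product = 11q, which adds 11q/33 to that product's percentage.
- Chance of at least one = 1 − (1 − q)^33.

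| q (assumed) | Extra subjects overall | Extra per product | Points added per product | Chance of at least one |
|---|---|---|---|---|
| 1% | 0.33 | 0.11 | 0.3 | 28% |
| 5% | 1.65 | 0.55 | 1.7 | 82% |
| 10% | 3.3 | 1.1 | 3.3 | 97% |
| 20% | 6.6 | 2.2 | 6.7 | 99.9% |

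Under the protocol wording every extra is 0.

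**The case against.** The strongest reply is that this is a small wording difference with little consequence. Safety is summarized by counts and percentages, with no test or threshold. The SAP rule can only add TEAEs, so it errs on the cautious side, and the balanced sequences spread the additions. The product-related row rests on the investigator's causality judgment, which must weigh timing, and every AE is listed. Dating by calendar day is also a defensible convention where onset time is not collected. The protocol records the time of brushing ("The date and time of each dose/application/administration will be recorded in the source documents", or directly in the CRF), but neither document shows that the AE form records onset time. For serious events, Protocol 10.4.2 asks only for the date of onset.

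Most of this stands, and it limits the size of the point. It does not remove the conflict between the documents, the incorrect declaration in SAP Section 5, or the missing product rule.

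A reader might infer more than the documents support:

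- **That everything found before brushing at Visit 2 becomes a TEAE.** A finding given an earlier onset date is excluded under both wordings.
- **That the event certainly falls to the first product.** That is one reading; SAP 4.1.3 yields no product.
- **That the examinations before brushing at Visits 4 and 6 are misassigned too.** The added words about date concern only first use in the study. At those visits the last product received is the previous one, and SAP 4.5 itself refers to onset date and time. The Listing 16.2.7.1 shell shows dates only, but a listing layout does not define the derivation.
- **That one event distorts a period-1 rate.** Table 14.3.1 is by product and overall, not by period.

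**Conclusion.** The point holds in a narrow form. SAP 4.5 departs from Protocol 12.3.4 without declaring it. It counts as treatment emergent any AE with recorded onset on the Visit 2 date but before brushing, and it leaves that event's product either the first one or undefined.

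The consequence is a modest over-count of descriptive TEAEs. Nothing in the documents suggests that it favors one product or changes an efficacy conclusion. The 3.0 points per subject assumes all 33 receive the product. The expected counts rest on assumed rates of 1% to 20% and on assignment by date. The correction is worth making because oral tolerability is the only safety objective and the change is cheap.

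**What to change.** 1. In SAP 4.5, restore the protocol's definition, so that treatment emergence starts at the first use of study product.
2. Add that AEs recorded at the Visit 2 assessments before brushing are not treatment emergent. Use onset time against application time if the CRF collects onset time. Otherwise use whether the AE was recorded at the pre-brushing assessment. Protocol 8.2.1 also records AEs after brushing at Visit 2 (step 10), so any record that does not show which assessment it came from should be settled at the blind data review.
3. For Visits 4 and 6, cross-refer to the rule in SAP 4.1.3 that assigns an event to the last product received before it. No new rule is needed.
4. Add onset time to Listing 16.2.7.1 only if it is collected.

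If the sponsor prefers the date rule, it should be declared in SAP Section 5, and SAP 4.5 should state the product for an event before first brushing.

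The cost is a few lines of SAP text and one programming condition, made before unblinding. The protocol text does not change. The fallback in item 2 means that onset time need not be newly collected.
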